For analysis (ii) we only compute power for the effect of Post, the effect of a clinic receiving the intervention and entering the post period, for the analysis of the entire sample. The method of computing the power for this stepped-wedge design (SWD) with unequal standard deviations in the prior and post time-periods is to first determine the design-effect for the SWD and then compute the power for a two-population comparison using the effective-sample-sizes based on the design-effect. The design-effect is estimated using the expression in Woertman et al (2013), also described in Hemming (2016). Because hospital and practice group are cross-classified across the four SWD groups, and because little is known about likely levels of interclass correlation coefficients (i.e., the level of clustering) for each of hospital, practice-group and clinic, we perform illustrative power calculations assuming that the net impact of clustering is equivalent to hospital-level clustering alone with an ICC of hospital of 0.05. Based on results for past cluster-randomized studies at the clinic level, an intraclass correlation of 0.05 appears to be a conservative estimate of clustering by clinic^{66,67} and so it is not unreasonable for 0.05 to still be conservative once the upper-level sources of cross-classified clustering are absorbed. The other inputs are 70 practices (clusters), 4 waves of intervention onset, no-baseline period, 1,696 patients in total and equal numbers of patients per clinic per time-interval. Under this scenario the design-effect is 2.385. Therefore, the effective sample-size (ESS) is 711.

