The second part of the calculation is to determine the power of a two-group comparison of a continuous outcome in the absence of clustering when the total sample-size is 711. Because there are 10 group-times in the post-period and 6 in the pre-period each with 106 observations, the split in the ESS between the post and the pre period is 444 and 267. The mean and standard deviation of the outcome in the pre-period is given by the above values for ED admissions; the mean is 85 and the standard deviation is 83. To determine the mean and standard deviation of the outcome expected in the post period, we take weighted averages of the DA and ED admission means and standard, using the total theorem of probability to compute marginal effects. The weight of DA to total patients is 19/106 = 0.094. The weighted average marginal mean and weighted average marginal standard deviation of the observations in the post period are 76.93 and 84.99, respectively. Because the sample-sizes are reasonably large, an asymptotic normal approximation is well justified (i.e., the true distribution of the outcome is bimodal will be averaged out). Given the ESS's and these means and standard deviations, a two-sided 0.05-level test has power of 0.23. In order to have 0.80 power, we would need a much larger effect-size. Specifically, the mean for the post-period would need to be approximately 66.5. Due to the small fraction of ED patients, this will only be plausible if there is a spillover effect of the intervention such that the outcome reduced for DA and ED patients, not just for DA patients.

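### Analysis (ii) power: the post-period SD should be 78.06, 19/106 is 0.179, and the printed inputs give a design effect of 2.112, not 2.385; power stays low (about 0.28 against 0.23)

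*Combined protocol and SAP*

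**What the plan says.** Section D.8 of the Research Plan gives the power for analysis (ii) in two steps.

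- **Design effect.** The plan takes clustering to be "equivalent to hospital-level clustering alone with an ICC of hospital of 0.05". It then lists the remaining inputs: "The other inputs are 70 practices (clusters), 4 waves of intervention onset, no-baseline period, 1,696 patients in total", with equal numbers in every clinic and interval. The result is "Under this scenario the design-effect is 2.385", hence an effective sample size (ESS) of 711.
- **Two-group comparison.** With 10 post and 6 pre group-periods, "the split in the ESS between the post and the pre period is 444 and 267". The pre-period takes the ED values (mean 85, SD 83). The post-period is a mixture of direct and ED admissions: "The weight of DA to total patients is 19/106 = 0.094". Its moments are reported as follows: "The weighted average marginal mean and weighted average marginal standard deviation of the observations in the post period are 76.93 and 84.99, respectively".

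From these the plan concludes that "a two-sided 0.05-level test has power of 0.23", and that for 0.80 power "the mean for the post-period would need to be approximately 66.5". It says openly that such a mean is plausible only if the intervention also shortens times for ED patients.

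**The concern.** Three printed figures do not follow from the inputs beside them: the post-period SD, the decimal value of the weight, and the design effect. The SD is suspicious on sight. Replacing about 18% of a group with SD 83 by patients with SD 28 should reduce the spread unless the gap between the means is large, yet the printed SD rises to 84.99.

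This is the plan's only power calculation for the randomised contrast, and the only source for how large a spillover effect would be needed. A reader should be able to reproduce it. The calculation also treats the pre-crossover period as entirely ED admissions, whereas the current Figure 2b shows direct admissions in cells that come before crossover.

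**Working it through.** **Inputs.** From D.8: ED 85 min (SD 83); direct admission (DA) 40 min (SD 28); two-sided alpha 0.05; ICC 0.05; 70 practices, 4 waves, no baseline, N = 1,696, equal cells; ESS split 10:6. From Figure 2a: 19 DA and 87 ED per post-crossover cell.

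**1. The plan's power from its own intermediates.** SE = √(84.99²/444 + 83²/267) = √(16.27 + 25.80) = 6.49. The difference is 85 − 76.93 = 8.07. Power = Φ(8.07/6.49 − 1.96) + Φ(−8.07/6.49 − 1.96) = 0.238. The post mean for 0.80 power is 85 − (1.960 + 0.842) × 6.49 = 66.8. These agree closely with the printed 0.23 and 66.5.

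**2. Weight.** 19/106 = 0.1792, which also equals 190/1,060 from the D.8 post-period counts (190 + 870). The mean is 85 − 45 × 0.1792 = 76.93, as printed. A weight of 0.094 would give 80.77. The fraction is therefore right, the decimal is wrong, and the decimal did not enter the calculation.

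**3. Post-period SD.**
- Within-group variance: 0.1792 × 28² + 0.8208 × 83² = 5,794.7.
- Between-group variance: 0.1792 × 0.8208 × 45² = 297.9.
- SD = √6,092.6 = **78.06**.
- With weight 0.094 the SD would be 80.55, so neither weight gives 84.99.
- Adding the squared deviations unweighted reproduces the printed value: √(5,794.7 + 36.93² + 8.07²) = 84.99.

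**4. Design effect.** Patients per practice-period: n = 1,696/(70 × 4) = 6.06. With k = 4 steps, no baseline and ρ = 0.05, the stepped-wedge design effect is

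{[1 + ρ(kn − 1)] / [1 + ρ(kn/2 − 1)]} × {3(1 − ρ) / [2(k − 1/k)]} × k = (2.161/1.556) × 0.380 × 4 = **2.112**.

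The generalised least squares (GLS) variance of the Post coefficient, with period fixed effects and a practice random intercept on the Figure 2a layout, gives the same 2.112 relative to an equal-split comparison. The result therefore does not depend on how the cited expression is read. ESS = 1,696/2.112 ≈ 803. At this cell size the design effect peaks at 2.29 (ICC 0.136), so no ICC yields 2.385.

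**5. Effect on power** (10:6 split kept, as in the plan):

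| ESS | Post SD | SE | Power | Post mean for 0.80 power |
|---|---|---|---|---|
| 711 | 84.99 | 6.49 | 0.24 | 66.8 |
| 711 | 78.06 | 6.29 | 0.25 | 67.4 |
| 803 | 84.99 | 6.10 | 0.26 | 67.9 |
| 803 | 78.06 | 5.92 | 0.28 | 68.4 |

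**6. Figure 2b.** The crossover sequence is taken from Figure 2a.
- Pre-crossover DA: Group 2, 6; Group 3, 2 + 1; Group 4, 6 + 5 + 10. Total 30, with 578 ED: 30/608 = 4.9%.
- Post-crossover DA: 63 + 34 + 13 + 44 = 154, with 817 + 497 + 383 + 330 = 2,027 ED: 154/2,181 = 7.1%.

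Each cell was given the mean 85 − 45 × (its DA share), and the model (ii) contrast was estimated by GLS with 18 equal clinics per group and ICC 0.05. The expected reduction is 1.6 min over the four rollout blocks (SE about 5.4) and 1.9 min with the maintenance block (SE about 5.3). Power is about 0.06 in both cases.

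**The case against.** The strongest defence is that nothing depends on these figures. The plan calls the calculation illustrative, reports inadequate power candidly, and sets no sample size, model or decision by it. Both numerical errors are conservative, and the misprinted decimal changed nothing. All of that stands, and it keeps the point minor. It does not make the printed SD or design effect correct.

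Some stronger inferences are tempting but not supported:

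- **That the cluster level or cell size is unstated, or that three hospitals were the clusters.** D.8 enters 70 practices with equal cells, which fixes n at 6.06. D.4 places practices from every hospital at each step, D.5 and D.8 describe hospitals as cross-classified with the stepped-wedge groups, and model (ii) fits hospital as a fixed effect. A three-cluster calculation is not a valid reading. What remains is that the hospital-level wording sits badly beside the practice-level input.
- **That the source of 2.385 is known.** It is not. The accurate statement is that the printed inputs do not give it.
- **That the Figure 2b contrast is about 1 min.** That is the crude pooled difference (82.78 − 81.82 = 0.96). Model (ii) adjusts for period and clinic and gives 1.6 to 1.9 min.

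It can also be said that D.8 belongs to the original design and that re-running power on largely accrued data is optional. That is fair: Figure 2b is a matter of currency, not an arithmetic error, and a short statement is enough.

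**Conclusion.** The point holds, at minor severity. The SD is a formula error, the decimal is a harmless misprint, and the design effect cannot be reproduced from the stated inputs. Correcting the SD and design effect together raises power by about 0.04 over the plan's intermediates (0.24 to 0.28) and eases the required post-period mean by about 1.6 min (66.8 to 68.4). A reader might infer that the errors undermine the plan's conclusion. They do not: power stays far below 0.80 in every row of the table, and the dependence on spillover is unchanged.

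The corrected figures rest on the plan's means, SDs, ICC, equal cells and 10:6 split. The Figure 2b result rests on more: Figure 2a's crossover order (Figure 2b's shading is not visible in the text available), 18 equal clinics per group, the same ICC, and the plan's own projections for the 27- and 36-month blocks. Equal clinics are a rough approximation in the maintenance block, which covers only two hospitals. The documents do not explain the pre-crossover direct admissions, which do not fit the statement in D.3 that practices awaiting the intervention contribute only ED admissions.

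**What to change.** In section D.8:

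1. Print 19/106 as 0.179 and the post-period SD as 78.06.
2. Replace the design effect and ESS with 2.112 and about 803, or show the inputs that give 2.385.
3. Restate power as about 0.28 and the post mean needed for 0.80 power as about 68.4 min. If ESS 711 can be justified, these become about 0.25 and 67.4 min.
4. Reword the hospital-level clustering assumption so that it agrees with the 70 practices entered as clusters.
5. Add a sentence that, under the Figure 2b counts, the expected contrast and power are far lower than in the original calculation, and state the assumptions used.
6. Keep the statement that analysis (ii) is underpowered without spillover.

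The cost is a text correction and one short recalculation. Design, sample size and models do not change.

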Finally, the health outcomes shown were prioritized by these same stakeholders.³⁹ Accordingly this conceptual framework reflects a process of intensive stakeholder engagement in the development of our research question and in selecting our primary and secondary outcomes. **From this Conceptual Framework, our Causal Model may be summarized as follows**: We hypothesize that, by eliminating ED wait times, exposure to the often hectic ED environment, and reducing the number of healthcare teams involved in care provision, directly admitted children will have reduced time to clinical care and improved experiences. The relative benefits of direct admission may differ based on medical complexity, with complex patients, often well known to the hospital-based healthcare teams, more likely to receive timely, personalized care. Primary reason for hospitalization may also influence timeliness of care provision, with conditions requiring minimal diagnostic testing prior to treatment initiation (for example UTIs and SSTIs) having the greatest benefit from direct admission.^{29,35}

3. Comparators. This study will involve a comparison of outcomes in children who are admitted from eligible primary care practices where the direct admission intervention is available (including children admitted directly and through EDs) to those admitted from practices not yet eligible for the intervention (hence all ED admissions). Both ED and direct admission are in current clinical use, with national statistics showing that 25% of children with unplanned hospitalizations are admitted via direct admission while 75% are admitted through EDs.⁵ Children who are transferred from another hospital (inter-hospital transfers) will be excluded, given our inability to account for types and duration of healthcare received at the transferring hospital. All hospitals in the US that receive reimbursement from the Centers for Medicare and Medicaid Services are required to document this variable on Universal Billing forms, and the validity of this variable has been demonstrated in two previous studies.^{46,47}

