achieve our research objectives, primary and urgent care practices at each hospital will be randomized to cross over from ED admission to the direct admission intervention using a cluster-randomized stepped wedge design (SWD). The direct admission intervention will be sequentially deployed to 4 groups of practices as shown in Figure 2. This crossover will be unidirectional and occur at 4 time points, with the first two blocks being six months in duration, and the second two blocks being nine months in duration given relatively slow enrollment during the COVID-19 pandemic. Additionally, to increase the number of children in the direct admission arm, we will continue to evaluate the direct admission program during a 9-month maintenance block (months 37-45) at NCH and PRMC-E following the current approach to recruitment and enrollment . Because of

Figure 2. a) Original design: Characteristics of stepped wedge cluster randomized controlled trial, where shaded areas indicate direct admission intervention exposure and unshaded areas indicated control conditions

	TIME (0-36 i	month proje	ect period; e	each block re	epresents 6	months)
	0 mo	6 mo	12 mo	18 mo	24 mo	30 mo
Group 1 (18		DA: 19	DA: 19	DA: 19	DA: 19	
practices)		ED: 87	ED: 87	ED: 87	ED: 87	
Group 2 (18	Pre-	DA: 0	DA: 19	DA: 19	DA: 19	Post-
practices)	rollout	ED: 106	ED: 87	ED: 87	ED: 87	rollout
Group 3 (17	period	DA: 0	DA: 0	DA: 19	DA: 19	period
practices		ED: 106	ED: 106	ED: 87	ED: 87	
Group 4 (17		DA: 0	DA: 0	DA: 0	DA: 19	
practices)		ED: 106	ED: 106	ED: 106	ED: 87	
Rollout period						

(DA = direct admission; ED = ED admission; numbers indicate projected sample size)

b) Modified design given reduced hospitalization volumes during the COVID-19 pandemic, with the 18 and 24 month steps extended to 9 months each, and addition of a 9-month maintenance block (months 37-45).

are projections estimated from enrollment to date)							
	0 mo	6 mo	12 mo	18 mo	27 mo	36 mo	45-50
				(9 mo	(9 mo	(9 mo	mo
				step)	step)	step)	
Group 1		DA: 8	DA: 8	DA: 23	DA: 12	DA: 12	
(18		ED: 129	ED: 92	ED: 216	ED: 232	ED: 148	Post-
practices)	Pre-						rollout
Group 2	rollout	DA: 6	DA: 12	DA: 12	DA: 5	DA: 5	period
(18	period	ED: 85	ED: 61	ED: 147	ED: 172	ED: 117	
practices)							
Group 3		DA: 2	DA: 1	DA: 5	DA: 5	DA: 3	
(18 practices		ED: 132	ED: 66	ED: 153	ED: 145	ED: 85	
Group 4		DA: 6	DA: 5	DA: 10	DA: 22	DA: 22	
(18		ED: 91	ED: 56	ED: 148	ED: 182	ED: 148	
practices)							

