TIME (0-50 month project period; each block represents 6 months unless otherwise specified; the 27mo and 36mo blocks are projections estimated from enrollment to date)

-----Rollout period-----Maintenance

pcori

PRINCIPAL INVESTIGATOR: [name]

very minimal program updake at CHP, we will not evaluate program maintenance at CHP. Figure 2b summarizes our anticipated additional recruitment of patients admitted directly and via emergency department admission at NCH and

PRMC-E, with numbers estimated from actual enrollment to date.

We will randomize 70 primary and urgent care practices: 18 at NCH, 34 at CHP, and 18 at PRMC-E (*Please see LOS from PCP practices affiliated with each hospital*). Practices in each group will be randomized using a stratified approach, with 17-18 practices (4-9 practices per hospital) randomized to crossover to the direct admission intervention at each step/crossover point, stratified by hospital and practice group. Given the closure or merger of 3 practices during the first project year, an additional 2 practices will be randomized to either Group 3 or Group 4, beginning during the 18 month block (Block 3).

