When estimating the model in (i), for our primary analysis we plan to only use observations from the post-period. This avoids any contamination from outcomes of ED observations when DA was not available. However, to gain some insight into the closeness of the results from this analysis with those that we'd expect to see if it was possible to have patient-level randomization, in a supplemental analysis we will include the pre-intervention ED observations and test if there is a change in the mean ED outcome in the post-intervention period. A result consistent with minimal change over time will support a finding that, in the absence of the intervention, the outcomes for DA patients would have been the same as those observed for ED patients.

The statistical model for analysis (ii) has a similar form:

$$Y_{ijht} = \beta_0 + \beta_1 Post_{jht} + \beta_2 x_{ijht} + \beta_{3t} + \beta_{4h} + \theta_{jh} + \varepsilon_{ijht}$$

differing only in that the direct admission indicator is replaced with $Post_{jht}$, a time-varying practice within hospital indicator of whether the intervention has been rolled-out (1 = intervention transition has occurred by time period t and 0 = direct admission intervention has not occurred by time-period t). The key coefficient of interest is β_1 , which captures the structural shift in the outcome that occurs when a practice receives the direct admission intervention. Because $Post_{jht}$ does not vary within a clinic and time-period, the information in the observations made within a clinic and time-period depends on the size of the effects of clinic and time-period with the statistical significance of inferences about β_1 is likely to be reduced by the clustering of observations in clinics. An additional component of clustering arises because the four groups are aligned with nine practice groups that in turn are embedded in three hospitals. We acknowledge that there may be separate levels of clustering in the data due to hospital and below that due to practice groups.

However, the nine practice groups emanating from the 3 hospitals will be randomly distributed across the four groups of the stepped-wedge design in a manner that balances the four groups with respect to the characteristics of these groups. Because the practice groups and hospitals are cross-classified with the SWD groups, their effects on the statistical precision of the results will be much less than under a purely hierarchical arrangement.

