until thematic saturation is reached.⁵⁸ Interviews will be recorded with permission and transcribed verbatim, and analyzed iteratively (concurrent with ongoing qualitative work) using a general inductive approach.^{59–61} Analysis will be led by Drs. [name] and [name], in partnership with [name] (Co-investigator, Years 1-3), [name] (Years 3-5), [name] (Years 3-5) and [name] (Parent partner). Results summaries will be shared with interview participants, and with hospitals' DALTs, both to return results to participants and to member-check the credibility of findings.^{62,63}

6. Study Population and Setting

Eligibility Criteria. We will limit our analysis to children < 18 years of age admitted with the following common medical reasons for hospitalization: gastroenteritis/dehydration, skin and soft tissue infection, UTI, pneumonia, viral infection not otherwise specified, and influenza. These diagnoses comprise approximately 25% of all unscheduled PHM admissions nationally, and represent conditions that have been identified as appropriate for direct admission but not currently accepted for direct admission at the participating hospitals.^{25,39} Children with planned admissions (i.e. chemotherapy), those admitted to non-PHM Services (i.e. the ICU), and those transferred from other hospitals will be excluded.

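### Section D.8 was not updated for the modified design: the analysis (ii) power of 0.23 and the analysis (i) sizes of 190 and 870 come from Figure 2a, while Figure 2b's partly projected cells give analysis (ii) power of about 0.05 to 0.14

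*Combined protocol and SAP*

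**What the plan says.** Section D.8 sizes both Aim 1 analyses. For analysis (i), direct admission (DA) against ED admission at patient level, it counts 190 direct and 870 concurrent ED admissions; Section D.5 says "for our primary analysis we plan to only use observations from the post-period". For analysis (ii), the effect of a practice having crossed over, it uses 16 group-by-period cells of 106 children (10 post, 6 pre), 1,696 children in all, and a design effect of 2.385. The pre-period mean is the pure ED value. The conclusion is that "a two-sided 0.05-level test has power of 0.23", and that 0.80 would be plausible only with spillover to ED patients.

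Section D.4 describes an intervention "sequentially deployed to 4 groups of practices" and then replaces the layout. Figure 2b is headed "Modified design given reduced hospitalization volumes during the COVID-19 pandemic": two steps are lengthened to nine months and a nine-month maintenance block is added. Its note says that "the 27mo and 36mo blocks are projections estimated from enrollment to date". For one of the three hospitals, "we will not evaluate program maintenance at CHP".

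Section D.3 describes the controls as "those admitted from practices not yet eligible for the intervention (hence all ED admissions". Section D.6 describes the study diagnoses as "not currently accepted for direct admission at the participating hospitals".

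**The concern.** Section D.8 and Figure 2b are both current text, and they describe different trials. The analysis (ii) power depends on how far the share of direct admissions rises at crossover. Figure 2a assumes a rise from 0 to 17.9%. Figure 2b shows a lower share after crossover and, in groups that have not yet crossed over, a share above zero. Both shrink the contrast. Section D.5 says how the model codes the longer blocks, but power is not recomputed anywhere.

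At stake is how a null analysis (ii) is read. A reader of Section D.8 would take it as a test with an expected effect of about 8 minutes and power near one in four, against a control condition without direct admissions. Figure 2b supports neither.

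**Working it through.** **Inputs.** Section D.8: ED mean 85 min (SD 83), DA mean 40 min (SD 28), hence a 45-minute difference; two-sided 0.05; ICC 0.05; design effect 2.385. Figure 2b, five blocks in order:

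| Group | DA | ED |
|---|---|---|
| 1 | 8, 8, 23, 12, 12 | 129, 92, 216, 232, 148 |
| 2 | 6, 12, 12, 5, 5 | 85, 61, 147, 172, 117 |
| 3 | 2, 1, 5, 5, 3 | 132, 66, 153, 145, 85 |
| 4 | 6, 5, 10, 22, 22 | 91, 56, 148, 182, 148 |

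Totals: 184 DA, 2,605 ED, 2,789 children. The last two blocks are projected.

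**1. The plan's figures.** Section D.8 uses Figure 2a: 10 × 19 = 190 DA; 10 × 87 = 870 post-crossover ED; 870 + 6 × 106 = 1,506 ED. With effective sizes 267 and 444, SE = √(83²/267 + 84.99²/444) = 6.49; difference 85 − 76.93 = 8.07; power (both tails) 0.238. The stated 0.23 reproduces to rounding.

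**2. Two slips in the same paragraph.** 19/106 = 0.179, not 0.094. The mean of 76.93 uses 0.179 (85 − 45 × 0.179 = 76.93; 0.094 would give 80.77). The total-variance SD with w = 19/106 is √(w·28² + (1−w)·83² + w(1−w)·45²) = 78.06, not 84.99. Correcting the SD alone gives 0.25 for the original design.

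**3. Figure 2b by crossover status.** Its shading is not visible, so Figure 2a's order is used (group 1 from the first block, group 2 from the second, and so on).
- Pre-crossover: DA 6+2+1+6+5+10 = 30 and ED 578, so 30/608 = 4.9%. All six cells contain DA, and all lie in blocks not labelled as projected.
- Post-crossover: 154/2,181 = 7.1%; 112/1,641 = 6.8% without maintenance; 68/866 = 7.9% in the three blocks not labelled as projected. Of the 154, 86 are projected.
- Whatever the order, all four groups show DA in the first block (8, 6, 2, 6; sum 22). Only one group has crossed over by then, so at least 22 − 8 = 14 precede crossover.

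**4. Analysis (ii), the plan's two-group method.** Post mean 85 − 45 × 0.0706 = 81.82. The pre mean is 85 − 45 × 0.0493 = 82.78 if control-period DA gain the full 45 minutes (case A). It is 85 if they have ED-like times or are set to zero (case B). SDs are as in step 2.

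| Cells used | Case A: difference; power | Case B: difference; power |
|---|---|---|
| Five blocks, design effect 2.385 | 0.96 min; 0.053 | 3.18 min; 0.084 |
| Five blocks, no clustering | 0.96 min; 0.057 | 3.18 min; 0.134 |
| Without maintenance, 2.385 | 0.85 min; 0.052 | 3.07 min; 0.080 |
| First three blocks, 2.385 | 1.31 min; 0.055 | 3.53 min; 0.082 |

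**5. Model-based check.** Generalised least squares with period effects and a random clinic intercept, on expected cell means 85 − 45 × (DA share), assuming 18 equal clinics per group, SD 80 and ICC 0.05:

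| Blocks | Case A | Case B |
|---|---|---|
| Three | 0.054 | 0.089 |
| Four | 0.061 | 0.113 |
| Five | 0.065 | 0.126 |

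Over ICC 0 to 0.20 the range is 0.053 to 0.072 in case A and 0.074 to 0.144 in case B. With 36 of 70 clinics in the last block (18 + 18 at the two maintenance hospitals), case A gives 0.063 to 0.064. Over all 24 possible crossover orders at ICC 0.05, the maximum is 0.071 in case A; the same run for case B gives at most 0.134.

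**6. Analysis (i).** SE of the difference = √(28²/n_DA + 83²/n_ED): 2.91 min for 154 v 2,027; 3.39 for 112 v 1,529; 4.49 for 68 v 798. Against 45 minutes, power exceeds 0.99 each time.

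**The case against.** The strongest objection concerns how control-period direct admissions are valued. The 40-minute mean comes from a single outside hospital with a mature programme. Direct admissions before crossover precede the standardised process, and Section A warns that unstructured direct admission may cause delay. Giving them the full 45 minutes is therefore one assumption among several. This stands. A reader might infer that analysis (ii) is simply at its type I error rate, but that holds only under case A, so the range must run to about 0.14.

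Two further limits also stand. Sections D.1 and D.6 describe baseline direct admission rates as low, not zero, so some control-period direct admissions are unsurprising. What needs reconciling is the ED-only wording in Section D.3 and the wording on diagnoses in Section D.6. And 190 and 1,506 are both labelled as targets in Table 5, so expecting more ED admissions than the target is not itself an error.

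A reader might also infer that Table 5's 2,288 potentially eligible children contradicts Figure 2b's 2,789. It does not: 2,288 covers two years and Figure 2b covers 6 + 6 + 9 + 9 + 9 = 39 months. Prorated, 2,288 × 39/24 = 3,718, which is above 2,789. The design effect of 2.385 cannot be checked from the documents, because its expression is cited and not printed; the result does not depend on it.

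Finally, Section D.8 calls its calculation illustrative and already concedes low power. That limits the consequence, but it does not make 0.23, 190 and 870 correct for the current design.

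**Conclusion.** The point holds in this form. Section D.8 reports the power and sample sizes of a superseded layout. From Figure 2b's published cells, without spillover and at the plan's 45-minute difference, analysis (ii) power is about 0.05 to 0.07 if control-period direct admissions gain the full benefit, and about 0.07 to 0.14 if they gain none or are set to zero. Either way it is well below 0.23. Analysis (i) has about 154 direct and 2,027 ED admissions (112 and 1,529 without maintenance).

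This rests on Figure 2a's crossover order, on two projected blocks, on equal clinics within groups in the model-based check, and on the plan's means and SDs carried over unchanged. Hospital effects cannot be modelled from Figure 2b, so these are ranges and not replacement values.

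A reader might infer that the trial cannot answer its patient-level question. The documents do not support that: analysis (i) keeps power above 0.99. Nor do they show that the control-period direct admissions reflect a breach of the randomised schedule; they do not explain them. The plan's conclusion that analysis (ii) is weak without spillover is unchanged. This should be fixed, but it does not call for a change of design.

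**What to change.** - Recompute Section D.8 for Figure 2b from practice-level counts by actual crossover status, with only the two maintenance hospitals in the last block.
- Restate the analysis (i) sizes. Give the analysis (ii) power as a range (about 0.05 to 0.14 from the published cells), saying how control-period direct admissions are treated and which inputs are projected.
- Correct 0.094 to 0.179 and 84.99 to 78.06.
- Reconcile the ED-only control wording in Section D.3 and the statement on study diagnoses in Section D.6 with the control-period direct admissions in Figure 2b.
- Put Table 5 on the 39-month enrolment basis, or label 190 and 1,506 as original-design targets.
- State that a non-significant analysis (ii) is not evidence of no effect.

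The cost is recalculation and wording. The stated power becomes less favourable; design, data collection and models stay as they are.
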